5.3.1. Wound Evaluation

Wound evaluation for data collection purposes will begin at the initial visit and thereafter during each visit at the outpatient centers where this study is going to be conducted. Wound Evaluation will include the following parameters (please also see sample Case Report Form (CRF) in Appendix D which will be used at each visit):

- Wound size (length, width and depth)
- Evaluation of Odor. Investigator assessment of wound odor will be captured via a 4-point categorical scale after each application.
- Percent of Necrotic Tissue. The percent of necrotic tissue will be assessed based on photos taken of the wound with eKare inSight® and visual confirmation from the Investigator to determine the percent covered with the necrotic tissue versus the total area of the wound. This will be entered in question six of the Bates-Jensen Wound Assessment Tool, as described in Appendix C.
- Pain Assessments. Pain will be assessed by the subject after the application (or re-application, for interim visits) of the dressing. Pain will be based on a 10-point Pain Score.
- Site Infections. Any infections at the wound site will be documented. In the event a participant develops an infection his/her participation in the study will discontinue, and the physician will implement appropriate treatment measurements.
- Bates-Jensen Wound Assessment Tool (BWAT). The BWAT will be administered to further characterize the wound. Please see Appendix C for BWAT.

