8.2. SAMPLE SIZE JUSTIFICATION

This is an observational study without a comparison group; therefore a formal power analysis is not feasible. Rather, the study will aim to collect data from 20 patients with evaluable data. The key analysis for the study is providing a quantitative estimate of debridement of necrotic tissue. To this end, a 95% confidence interval centered on the sample mean for necrotic tissue reduction will be created using the critical t value for this analysis; this will provide the best point estimate for debridement, as well as a measure of uncertainty, which will takes the sample size into account.

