8.3. ANALYSIS OF EFFICACY DATA

8.3.1. Primary Endpoint

Percent reduction in necrotic tissue will serve as the primary endpoint. The Investigator will analyze wound photographs and visually inspect the wound in order to calculate percent necrotic tissue and enter a value of 1-5, corresponding to:

- 1 = No necrotic tissue
- 2 = 0% - 25%
- 3 = 26% - 50%
- 4 = 51% - 75%
- 5 = 76% - 100%

The 95% confidence interval for the mean reduction in necrotic tissue across the study period will be evaluated to determine if the lower bound is positive, which would be an indication of significant reduction in necrotic tissue.

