8.3.2. Secondary Endpoints

- Percent patients with 100% wound closure in each group
- Number of new infections in wound site
- Change in wound volume over time, measured similarly to percent necrotic tissue; analyzed by providing the 95% confidence interval for the mean
- Mean odor score between groups; analyzed by providing the 95% confidence interval for the mean
- Mean pain score between groups; analyzed by providing the 95% confidence interval for the mean
- Mean BWAT score between groups; analyzed by providing the 95% confidence interval for the mea

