10.4 APPENDIX D: Case Report Form

Case Report Form (R16-017)

Subject Number:	Visit Date:	Visit Time:	AM	PM	Visit Type and Number:	
Height (inches):	Weight (lbs):	Age:				
Sex:  Male	 Female					
Race:  White	 Black	 Hispanic or Latino	 Asian	 Other/Mixed Race	 Native American	
Was mechanical debridement used?  Yes		 No				
Was a secondary dressing used?  Yes		 No	If yes, what kind? _____			
Wound Assessment						
Physical Examination and Wound Zoom Analysis			Bates – Jensen Wound Assessment Tool (BWAT)			

Diagnosis: _____
 
What is the percent of necrotic tissue? _____ %
 
Wound size (cm): Width _____ x Length _____ x Depth _____
 
Evaluation of odor: _____
 
 1  2  3  4
 
VAS Pain scale score within 10 minutes following dressing change: _____
 
 0  1  2  3  4  5  6  7  8  9  10
 
Site Infection: Yes No
 
If yes, discontinue subject and note steps taken:
			
1. Skin: _____
 
2. Depth: _____
 
3. Edges: _____
 
4. Undermining: _____
 
5. Necrotic Tissue Type: _____
 
6. Necrotic Tissue Amount: _____
 
7. Exudate Type: _____
 
8. Exudate Amount: _____
 
9. Skin Color Surrounding Wound: _____
 
10. Peripheral Tissue Edema: _____
 
11. Peripheral Tissue Induration: _____
 
12. Granulation Tissue: _____
 
13. Epithelialization: _____
 
TOTAL BWAT SCORE: _____
			

Place photograph of the wound from the Wound Zoom camera below:

Subject #: _____ **Date:** _____

*Please note that the information in the picture should match the above information.

Signature _____ **Date** _____

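### The primary endpoint is named as percent reduction in necrotic tissue, but Section 8.3.1 defines only a 1-5 category and never states the scale of the primary confidence interval

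*Combined protocol and SAP*

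**What the plan says.** - **Endpoint (Section 8.3.1).** "Percent reduction in necrotic tissue will serve as the primary endpoint". The Investigator is then to "calculate percent necrotic tissue and enter a value of 1-5", with 1 for no necrotic tissue and 2 to 5 for the bands 0-25%, 26-50%, 51-75% and 76-100%.
- **Analysis (Section 8.3.1).** "The 95% confidence interval for the mean reduction in necrotic tissue across the study period" is examined, and a positive lower bound is read as a significant reduction. No unit is given.
- **Purpose (Section 8.2).** "The key analysis for the study is providing a quantitative estimate of debridement of necrotic tissue". This section specifies a t-based interval, again without a unit.
- **Visits (Section 8.3.3).** Day 1 and the Final Visit are fixed as the two measurements, but no formula links them.
- **Measurement (Section 5.3.1).** The percentage comes from photographs and "visual confirmation from the Investigator to determine the percent covered with the necrotic tissue versus the total area of the wound". The next step is: "This will be entered in question six of the Bates-Jensen Wound Assessment Tool". That item is also a 1-5 category.
- **Case report form (Appendix D).** A numeric field asks "What is the percent of necrotic tissue", separately from the entry for item 6. No section says which of the two feeds the primary interval.
- **Secondary endpoint (Section 8.3.2).** "Change in wound volume over time, measured similarly to percent necrotic tissue", although volume is continuous and no bands for it are given.

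**The concern.** Three variables fit the text: the mean change in category, the mean change in percentage points of wound area, and the mean relative reduction from Day 1. They are different quantities. Section 8.3.1 points to a percentage by the name it uses and to a category by the only value it has the Investigator enter.

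This variable carries the study's only decision rule. It is also the main product of a single-arm study of 20 subjects with no power calculation. If the scale stays open, it can be chosen once the data are known. If the category is used, the result cannot be converted back to a percent reduction, and its size reflects where subjects started within and across the bands as well as how much tissue was removed.

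**Working it through.** **Inputs.** The bands are those of Section 8.3.1, with 0% scored as 1. Baselines are 20-100%, because Section 4.2.1 requires at least 20% necrotic tissue. n = 20 (Section 8.2). The documents give no expected mean, SD, power or target width, so there is no planned figure to reproduce. The half-width is t(0.975, 19) x SD / sqrt(20) = 2.093 x SD / 4.472 = 0.468 x SD, in whichever unit is chosen.

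**1. Does the score change determine the percent reduction?** Every whole-percent pair with a final value no higher than baseline was enumerated:

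| Score change | Percentage points | Relative reduction | Lowest or highest relative case |
|---|---|---|---|
| 0 | 0 to 24 | 0% to 96% | 25 to 1: 24/25 = 96% |
| 1 | 1 to 49 | 1.3% to 100% | 76 to 75: 1/76 = 1.3% |
| 2 | 26 to 74 | 34.2% to 100% | 76 to 50: 26/76 = 34.2% |
| 3 | 51 to 99 | 67.1% to 100% | 76 to 25: 51/76 = 67.1% |
| 4 | 76 to 100 | 100% | 100 to 0 |

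It does not. Expressing the category change as a percentage of the baseline category does not help. The lowest score is 1, so full clearance gives (2 - 1)/2 = 50% up to (5 - 1)/5 = 80%, never 100%.

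**2. Same treatment effect, different baselines.** A 50% reduction in every subject scores 0 for baselines 20-25%, 1 for 26-75% and 2 for 76-100%. Full clearance scores 1 from 20% and 4 from 100%.

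**3. Share of subjects with no score change.** Assume baselines spread evenly over the 81 whole percents from 20 to 100 and the same relative reduction in everyone, with final values rounded.
- 20% reduction: baselines 20-25, 32-50, 64-75 and 95-100 stay in their band. That is 6 + 19 + 12 + 6 = 43, and 43/81 = 53%.
- 30% reduction: baselines 20-25, 37-50 and 73-75 stay. That is 6 + 14 + 3 = 23, and 23/81 = 28%.
- Without rounding the shares are 45/81 = 56% and 25/81 = 31%.

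**4. One data set, three answers.** Take four subjects at each of 25 to 2, 24 to 3, 50 to 27, 75 to 52 and 100 to 77. The mean relative reduction is 55.8% (95% CI 42.1 to 69.6), the mean percentage-point change is 22.6 (22.2 to 23.0), and the mean category change is 0. The rule is met on both percent scales and fails on the category. This set was constructed to show the point and is not a forecast.

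**5. Decision rule under assumed inputs.** 20,000 trials of n = 20 were simulated with uniform baselines, normally distributed relative reductions, and final values rounded and limited to 0-100. The table gives the probability that the lower bound exceeds zero:

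| Mean, SD of reduction | Baselines | Percent reduction | Score |
|---|---|---|---|
| 20%, 30 | 20-60% | 80% | 60% |
| 20%, 30 | 20-100% | 87% | 79% |
| 20%, 40 | 20-100% | 69% | 70% |
| 20%, 50 | 20-100% | 55% | 63% |

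At mean 50% and SD 30, both are about 100%.

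**6. Bands against Appendix C.** For each whole percent from 0 to 100, the 8.3.1 bands and item 6 of the wound tool disagree only at 25% (2 against 3) and 75% (4 against 5). Section 5.3.1 nevertheless treats them as one entry.

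**The case against.** The strongest reply is that the category reading is not the only one, and may not be the intended one. The endpoint is named as a percentage, Section 8.2 promises a quantitative estimate, the camera computes tissue composition (Section 5.2.6), and the case report form has a numeric percent field. The wound-volume wording in 8.3.2 can also be taken to favour a continuous measure. On this view the data for the named endpoint will exist and only a cross-reference and a formula are missing. It can be added that a positive mean category change still shows improvement, that the simulation has no consistent direction and rests on invented inputs, that the 96% figure is a boundary case, and that percentage-point change also depends on baseline.

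Much of this stands. The endpoint can be computed, the defect is one of wording, and the simulation cannot show a bias in a known direction. The choice between relative reduction and percentage points belongs to the sponsor.

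It does not remove the problem. The instructions in 8.3.1 and 5.3.1 both end in a 1-5 entry, no section on the analysis names the numeric field, and no section gives a unit. Direction of change is not the named endpoint, nor the estimate that Section 8.2 calls the key analysis.

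**Conclusion.** The concern holds and should be fixed before any data are analysed. Section 8.3.1 names one quantity, defines another, and gives no scale for the interval. Followed as written, a mean category change does not estimate percent reduction: a change of 0 is compatible with up to 96% removal, and a change of 1 with anything from 1.3% to complete clearance. These ranges follow from the plan's own bands and entry criterion, taking whole-percent values.

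The no-change shares also assume evenly spread baselines and a uniform effect. The decision-rule probabilities rest on means and SDs that the documents do not supply. They show that the choice of scale can change the outcome in either direction, and that it makes little difference when the effect is large. The cut-point mismatch at 25% and 75% is minor.

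**What to change.** In Section 8.3.1:

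- Define the primary endpoint for each subject as 100 x (Day 1 - Final Visit) / Day 1. Compute it from the numeric percent field in Appendix D, assessed as Section 5.3.1 describes.
- State that a wound closed at the Final Visit is recorded as 0%, since a closed wound has no area from which to take a percentage.
- Build the planned t-based 95% interval on that variable and state its unit.
- Report the percentage-point change as supportive. Relative reduction is sensitive to worsening from a low baseline. A subject going from 20% to 60% counts as 100 x (20 - 60)/20 = -200%, and with 19 others at 50% the mean falls from 50% to (19 x 50 - 200)/20 = 37.5%.
- If the sponsor means percentage points, rename the endpoint and make that the primary variable.
- Keep the 1-5 score as supportive only, scored with the Appendix C item 6 cut-points, and delete the separate 8.3.1 bands.

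Add a cross-reference in Section 5.3.1 to the numeric field. Align the case report form's assessment block and photograph label, which name Wound Zoom, with the eKare camera named in Section 5.3.1.

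The cost is wording and a form label. No new data, visits or patients are needed.

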8.3.2. Secondary Endpoints

- Percent patients with 100% wound closure in each group
- Number of new infections in wound site
- Change in wound volume over time, measured similarly to percent necrotic tissue; analyzed by providing the 95% confidence interval for the mean
- Mean odor score between groups; analyzed by providing the 95% confidence interval for the mean
- Mean pain score between groups; analyzed by providing the 95% confidence interval for the mean
- Mean BWAT score between groups; analyzed by providing the 95% confidence interval for the mea

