5.3.5. TheraHoney® Foam Flex Application

The application of TheraHoney® Foam Flex will be performed according to the product labeling during the Initial Visit (Day 1) and subsequent Interim Visits. Dressing changes will take place daily, with the Investigator instructing participants on how to change the dressing at home on days when they do not visit the clinic. The use of secondary dressings will also be done at the discretion of an Investigator. At the discretion of an Investigator, use of TheraHoney® Foam Flex should be discontinued due to adverse events or lack of wound closure response.

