5.4. FINAL VISIT

The Final Visit will be scheduled to take place approximately 4 weeks following the Initial Visit. In the event that during a weekly Interim Visit, an Investigator judges the wound to be 100% healed and medical care is no longer necessary, that Interim Visit will be deemed the Final Visit.

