5.4.2. Physician Questionnaire

Product ease of use will be evaluated using on the Investigator Questionnaire (Appendix E) at the end of subject's study participation.

TABLE 5.1 TIME AND EVENTS SCHEDULE

REQUIRED ASSESSMENTS	SCREENING VISIT Day 0 (May be combined with first interim visit, Day 1)	INITIAL VISIT Day 1	INTERIM VISITS Approx. Every 7 Days	FINAL VISIT ⁵ Approx. 28 days after Day 1 visit
Informed Consent	X			
Demographics	X			
Medical History	X			
Concomitant Medication	X			
Physical Examination	X			
Doppler Assessment	X ^{1,3}			
Blood Glucose Assessment	X ^{1,2,4}			
Wound Screening Evaluation	X			
Confirmation of Eligibility	X	X	X	
Adverse Event Assessment	X	X	X	X
Wound Evaluation		X	X	X
Wound Photograph		X	X	X
TheraHoney® Foam Flex		X	X	
Secondary Dressing Notation		X ¹	X ¹	
Mechanical debridement noted		X ¹	X ¹	
Investigator Questionnaire				X

¹If required

²Within 30 days of screening visit or at screening visit

³Within 90 days of screening visit or at screening visit

⁴Diabetic subjects only

⁵Final visit may be an interim visit in the event patient heals fully before 4 weeks and no longer requires treatment

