8.3.3. Evaluable Dataset

An evaluable dataset will be used to conduct the efficacy assessments. This dataset will be defined as subjects who have at least a valid measurement for necrotic tissue from the Day 1 visit and their Final Visit, given that this will make up the measurement of the primary endpoint.

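### As written, the evaluable dataset drops subjects stopped for a wound infection at an interim visit but keeps early healers, which flatters both the infection count and the closure percentage

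*Combined protocol and SAP*

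**What the plan says.** Complete closure and "Number of new infections in wound site" are secondary endpoints in section 8.3.2, under the heading for efficacy data (8.3). Neither is given its own analysis set. Section 8.3.3 then says: "An evaluable dataset will be used to conduct the efficacy assessments". It defines that set as "subjects who have at least a valid measurement for necrotic tissue from the Day 1 visit and their Final Visit".

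Section 5.3.1 sets the consequence of infection: "In the event a participant develops an infection his/her participation in the study will discontinue". The case report form (Appendix D) repeats it beside the infection item: "If yes, discontinue subject and note steps taken".

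The Final Visit is planned about 4 weeks after the Initial Visit. Section 5.4 gives one exception, which applies when an Investigator "judges the wound to be 100% healed and medical care is no longer necessary, that Interim Visit will be deemed the Final Visit". Footnote 5 to Table 5.1 gives the same exception and no other. No section says how a visit at which a subject is discontinued is to be classed.

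Section 5.3.5 adds that, at an Investigator's discretion, use of the dressing "should be discontinued due to adverse events or lack of wound closure response". It does not say whether such subjects still attend a Final Visit.

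Section 8.4 summarises withdrawals and adverse events in all treated subjects, which it calls the safety population.

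**The concern.** The plan turns an early stop into a Final Visit when the wound has healed and is silent when the subject stops because of infection. Followed as written, the analysis set depends on outcome. Early healers stay in both numerator and denominator for closure. Subjects infected at an interim visit leave the set altogether, so their infection is not counted and they no longer count as non-closers. Both errors favour the product.

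The study has one arm, so there is no comparator in which a similar loss could offset this; the absolute estimates are the result. If an analyst must decide what a discontinuation visit is after seeing the data, the reported figures depend on that decision.

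**Working it through.** **Inputs.** Target of 20 evaluable subjects (8.2). The documents give no number to be treated, no dropout allowance, and no infection or closure rate, so there is no figure of the plan's own to reproduce. Let k be the number of further treated subjects discontinued for infection at an interim visit, taken as not closed, and x the number closed among the 20 evaluable. Both are assumptions.

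**Step 1: who is in the set.**
- Heals at an interim visit: that visit is the Final Visit (5.4), so the subject is evaluable.
- Infection at an interim visit: participation ends (5.3.1), with no Final Visit on the text of 5.4, so the subject is not evaluable.
- Infection first seen at the Final Visit: evaluable, and the infection is counted.

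**Step 2: infection count.** The endpoint omits all k interim infections. If none is first seen at a Final Visit, it reads 0/20 (exact 95% CI 0% to 16.8%). With k = 3, all treated subjects give 3/23 = 13.0% (2.8% to 33.6%).

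**Step 3: closure.** Reported x/20; in all treated subjects x/(20 + k). The ratio is (20 + k)/20 = 1 + k/20, whatever x is, provided at least one wound closes. Example with an assumed x = 8, reported as 40%:

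| k | Factor | All treated |
|---|---|---|
| 1 | 1.05 | 8/21 = 38.1% |
| 2 | 1.10 | 8/22 = 36.4% |
| 4 | 1.20 | 8/24 = 33.3% |
| 6 | 1.30 | 8/26 = 30.8% |

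For scale, the exact 95% CI for 8/20 is 19.1% to 63.9%. At k = 1 or 2 the shift is 1.9 or 3.6 points, small against that interval but always in the same direction.

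**Step 4: how large k might be (illustration only).** Assume a 4-week infection risk R, a constant weekly hazard over four looks with the fourth at the Final Visit, and ignore early healing. Then
- h = 1 − (1 − R)^(1/4)
- risk of an infection first seen at the Final Visit = h(1 − h)^3
- interim risk I = R − h(1 − h)^3
- expected k = 20 × I/(1 − I)
- closure factor = 1/(1 − I)

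| R | I | Infections uncounted (I/R) | Expected k | Factor |
|---|---|---|---|---|
| 5% | 0.0377 | 75.5% | 0.78 | 1.04 |
| 10% | 0.0760 | 76.0% | 1.64 | 1.08 |
| 20% | 0.1541 | 77.1% | 3.64 | 1.18 |
| 30% | 0.2347 | 78.2% | 6.13 | 1.31 |

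If instead 10% to 40% of infections are first seen at the Final Visit, 60% to 90% go uncounted, and the factor runs from 1.03 (R = 5%, 40% at the Final Visit) to 1.37 (R = 30%, 10% at the Final Visit).

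**The case against.** The exclusion is inferred. Sections 5.4 and Table 5.1 give healing as one case and do not say that a discontinuation visit cannot be final. Section 8.3.3 speaks of each subject's own Final Visit. Section 5.4.2 times the investigator questionnaire "at the end of subject's study participation", and Table 5.1 places that questionnaire in the Final Visit column alone, which suggests that the Final Visit is whatever visit ends participation. The case report form takes percent necrotic tissue on the same page as the infection, so the end value would normally exist and exclusion turns on the label alone. On this reading the effect is zero.

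This reading is reasonable, but the plan does not adopt it: the one rule it writes down for converting an interim visit covers healing only.

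Second, infected wounds are excluded at entry (4.2.2), so an on-study wound infection meets the adverse event definition (7.1) and is summarised in all treated subjects (8.4). That stands, and it means the safety information is not lost. It does not move the named endpoint out of 8.3, so a report could carry two different infection counts, and it does nothing for closure.

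Third, the closure shift is modest at low k, the larger factors need assumed infection risks that nothing in the documents supports, and neither endpoint has a test or success criterion. All of that stands and limits the weight of the point.

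Fourth, section 5.3.5 stops use of the dressing, not participation, so the loss of non-responders is only a possibility.

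Finally, the same undefined label also decides membership for the primary endpoint. That is a further reason to define it.

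**Conclusion.** The concern holds on the plan as written. Each infection found at an interim visit is missing from the 8.3.2 infection count, and closure is overstated by a factor of 1 + k/20 when 20 subjects are evaluable. The direction follows from the definitions and needs only one interim infection and, for closure, one closed wound. The size depends on an infection risk and timing that the documents do not give: over assumed 4-week risks of 5% to 30% with a constant hazard, about three quarters of infections go uncounted and closure is inflated by a factor of 1.04 to 1.31. If subjects stopped for lack of response also miss the Final Visit, the closure effect is larger. If a discontinuation visit is treated as the Final Visit, there is no effect from infection stops.

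The consequence is confined to descriptive estimates, with the safety signal kept in 8.4. The change should be made because the error runs one way and the remedy is cheap. Confidence is moderate, because of the second reading of the Final Visit.

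**What to change.** In sections 8.3.2 and 8.3.3:
- Analyse new wound-site infections and complete closure in all treated subjects, the population already defined in 8.4.
- Count subjects who discontinue without closure as not closed.
- State whether a discontinuation visit counts as the Final Visit for the evaluable dataset.

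The third item alone would keep subjects stopped for infection in both endpoints if the answer is yes. The first two make the result independent of that label and also cover subjects stopped under 5.3.5.

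The cost is one or two sentences. No new data are needed, because infection and wound status are already recorded at every visit, and no clinical rule changes. The reported infection count may be higher and the closure percentage lower.

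### New wound-site infections and 100% closure are reported without an interval or a clear denominator, and the infection count may leave out the subjects who became infected

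*Combined protocol and SAP*

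**What the plan says.** Section 8.3.2 lists six secondary endpoints. Four carry a 95% interval for the mean; wound volume, for example, reads "Change in wound volume over time, measured similarly to percent necrotic tissue; analyzed by providing the 95% confidence interval for the mean". The other two are "Percent patients with 100% wound closure in each group" and "Number of new infections in wound site", with no interval or other method. The infection line has no denominator.

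Three other places bear on how these two are computed:

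- Section 8.3.2 sits inside section 8.3, the efficacy analysis. Section 8.3.3 runs the efficacy assessments on subjects with valid necrotic-tissue values from both Day 1 and the Final Visit.
- Section 5.3.1 says: "In the event a participant develops an infection his/her participation in the study will discontinue".
- Section 8.4 bases safety analyses on all treated subjects and says that withdrawals and adverse events will be summarized. It names no interval.

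On size, section 8.2 says that "the study will aim to collect data from 20 patients with evaluable data". It gives no number to be treated and no target precision for any proportion.

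**The concern.** Two gaps combine.

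The first is the analysis set. Infection is an adverse outcome, but its place in the plan puts it under a rule that requires a Final Visit value. A subject discontinued for infection may not have one. The rule that selects the set is therefore linked to the event being counted, and the count can only be biased downwards.

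The second is precision. The plan has one arm and no comparator, so an interval is the main way to show how little a low count proves in about 20 subjects. The plan supplies intervals for four endpoints and leaves them off the two binary ones.

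Safety is a stated secondary objective (section 3.2). A report that followed the plan to the letter could print a low or zero infection count that excludes infected subjects, with nothing beside it to show what risk remains compatible with the data.

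**Working it through.** **Inputs.** The evaluable target is 20 (section 8.2). The confidence level is 95%, taken as two-sided because section 8.2 describes "a 95% confidence interval centered on the sample mean for necrotic tissue reduction will be created using the critical t value". The number treated is not stated; 20 to 30 is assumed. No expected infection or closure rate is given, so event counts below are illustrations. The plan has no figure of its own to reproduce, since 20 is set without a formula.

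**Step 1: can an infected subject be counted?** Section 5.4 and the footnote to Table 5.1 let an interim visit stand as the Final Visit only when the wound has fully healed. No such provision exists for a visit at which infection ends participation. Unless the infection is first seen at the Final Visit itself, or the site records the discontinuation visit as final, the subject fails section 8.3.3. Section 8.4 would keep the same subject. The documents do not say which set governs the infection line.

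Illustration: 22 subjects are treated, and 2 are discontinued for infection without a Final Visit value.

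| Set | Infections / N | Exact 95% interval |
|---|---|---|
| Evaluable (8.3.3) | 0/20 | 0% to 16.8% |
| All treated (8.4) | 2/22 = 9.1% | 1.1% to 29.2% |

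**Step 2: upper limit for a zero count.** Because infection ends participation, each subject contributes at most one infection and the count is binomial. For 0 events in n, the exact two-sided 95% upper limit is 1 − 0.025^(1/n).

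- n = 20: 1 − 0.025^(1/20) = 16.8%
- n = 22: 15.4%
- n = 25: 13.7%
- n = 30: 11.6%

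The one-sided 95% limit at n = 20 is 1 − 0.05^(1/20) = 13.9%.

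**Step 3: how often would a zero occur?** With 20 subjects, the chance of no infection is 0.95^20 = 36% at a true risk of 5% and 0.90^20 = 12% at 10%. A zero is more likely than not only if the risk is below 1 − 0.5^(1/20) = 3.4%.

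**Step 4: non-zero counts at n = 20 (Clopper-Pearson).** One event (5%) gives 0.1% to 24.9%. Four closures (20%) give 5.7% to 43.7%.

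**Step 5: which interval?** A t-interval at 0/20 has zero standard deviation and collapses to 0 to 0. At 1/20 the standard error is √(0.05 × 0.95 / 19) = 0.05 and the critical value is 2.093, so the interval is 5% ± 10.5%, or −5.5% to 15.5%. The plan does not propose a t-interval for these two endpoints. The step shows only why the method should be named when an interval is added.

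**The case against.** The strongest case against is that this is a minor reporting matter. Both endpoints are descriptive and secondary, no threshold is attached to either, and anyone holding a count and an N can compute an exact interval later. Section 8.4 also offers a route: a new wound-site infection appears to meet the adverse-event definition in section 7.1, so it should be summarized over all treated subjects in any case.

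Much of that stands. No data are lost, and the remedy can be applied at reporting. But section 8.3.2 does not promise an N for infection, section 8.4 does not promise an interval, and the two sections can yield different infection counts from the same trial.

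Several stronger readings are tempting and are not supported:

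- A reader might infer that infection is the plan's only numeric safety result. Section 8.4 also covers adverse-event incidence and withdrawal.
- A reader might infer that zero infections is the likely result. The documents give no expected rate, and Step 3 shows that a zero is the likelier outcome only below a risk of about 3.4%.
- A reader might infer that the plan would treat a zero as proof of safety. It states no such rule; the only decision rule is for the primary endpoint.
- A reader might infer that section 8.2 promises an interval for every endpoint. Its phrase "as well as a measure of uncertainty, which will takes the sample size into account" concerns the mean necrotic-tissue reduction only.

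**Conclusion.** The point holds. Two of six secondary endpoints have no interval, and the infection endpoint falls between an efficacy set that may exclude infected subjects and a safety set that would include them.

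For a zero count, infection risks up to 16.8% are not excluded if exactly 20 subjects are treated, falling to 13.7% at 25 and 11.6% at 30. These figures rest on a two-sided exact interval and on assumed numbers treated. How many infections the evaluable set would drop cannot be computed from the documents; it depends on whether infected subjects end up with a recorded Final Visit value.

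The primary analysis is unaffected. The correction is worth making because it settles which subjects are counted as well as adding an interval.

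**What to change.** In section 8.3.2:

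- Report infection as the number of treated subjects (the section 8.4 safety population) with a new wound-site infection, over all treated subjects, with a 95% Clopper-Pearson interval.
- Report closure as n/N with a 95% Clopper-Pearson interval, and state which subjects form N. An interval alone does not settle this: section 5.3.5 allows the dressing to be stopped for lack of closure response, and such subjects may also lack a Final Visit value.
- Report any zero count with its upper limit.

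The cost is a few sentences in the plan and two lines of analysis code, with no new visits or data. The downside is a slightly less favourable safety statement.
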